5. STUDY INTERVENTION

This study will have two study arms: The experimental intervention is T4C-MI and the control condition is Standard Prison Treatment and Programming.

5.a. Experimental Intervention

The research intervention is T4C-MI – Thinking for a Change for prisoners with mental illness. This intervention has two components. The first component is Thinking for a Change (T4C)¹, which is an established, manualized intervention shown to be effective at reducing behavioral infractions and time in administrative segregation among prisoners in the general population. T4C is a highly structured, 25-session, manualized intervention that is delivered in a closed-group format to 8-12 people up to twice a week over 12-14 weeks. The intervention curriculum includes three modules: (1) 10 sessions on social skills training that teach participants cognitive skills to interpret and respond positively to social situations that involve potential conflict; (2) 5 sessions on cognitive restructuring activities that teach participants a concrete process for self-reflection that is designed to help individuals identify and correct maladaptive or dysfunctional thought processes, such as anti-social thoughts, feelings, attitudes and beliefs that could lead to criminal activity; and (3) 10 sessions on problem-solving techniques which integrates the skills from the first two modules into a structured problem-solving method that can be used to manage interpersonally challenging situations. More information on this intervention can be found at in the treatment manual²⁶.

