The second component of T4C-MI is the Targeted Service Delivery Approach (TSDA)²⁶ that this research team developed to improve access to interventions like T4C for justice-involved persons with mental illness. The goal of the TSDA is to minimize the impact of neurocognitive and social impairments associated with mental illness on participants' ability to fully engage in and understand T4C's intervention materials. To achieve this goal the TSDA uses five therapeutic strategies during the delivery of T4C. These therapeutic strategies include repetition and frequent summarizing, amplification techniques, active coaching, low-demand practice, and techniques to maximize participation. The therapeutic strategies used in the TSDA are designed to work together during the delivery of the T4C to maximize participants' engagement with the intervention materials during each session. More information on the TSDA can be found in the publication²⁶.

5.b. Control Condition

People assigned to the control condition will receive standard prison treatment and programming. Standard prison treatment and programming includes any mental health services that participants are otherwise eligible to receive from the prison during the study time period. Prison mental health services include a range of treatment services that are designed to help people adjust to incarceration. These services include crisis services focused on addressing suicidal thoughts and behaviors and other mental health crisis; psychiatric evaluation, consultation, and medication management; and individual counseling to help to stabilize a prisoner's mental illness so he or she can function appropriately in the prison environment. Prison staff make all decisions regarding eligibility and allocation of all services and programming offered by the prison.

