6. STUDY PROCEDURES

Study participants will complete up to four, face to face interviews. The first interview is the screening interview where study eligibility is determined. Participants who meet the study eligibility criteria are enrolled in the study, randomized into one of the two study conditions. People who are randomly assigned to the experimental condition receive the study intervention and those who are randomly assigned to the control condition receive standard prison treatment and programming. All participants who are randomized to either study condition complete three additional follow up interviews: the baseline interview as well as 3- and 6-month interviews. Additionally, administrative data related to behavioral infractions and administrative segregation are collected at the 9-month time point.

6.a Description of Research Procedures

The study procedures are listed below.

All research interviews will take place in private locations in the prison:

First: Recruitment of study subjects will begin the month prior to the initiation of each intervention cycle. Correctional staff at the facility where the intervention is being delivered, will provide the research team with a list of all of the prisoners in their facility who meet the following criteria: a) 18 years and older: b) have mental health issues: c) have at least 1 year remaining on his or her prison sentence: d) do not have any restriction that would preclude the person from being in group gathering spaces within the prison; and e) do not have an intellectual or developmental disability.

Second: Research staff will go to the prison and invite potentially-eligible prisoners to meet with them in a private setting to learn about the study. During this initial meeting, research staff will provide participants with a flyer that describes the study and discuss potential participant's questions. The study flyer and discussions with potential participants will include information about the voluntary nature of the study and will explain that the person's decision about participation has no bearing on the person's criminal or civil cases. The research staff will also explain that the participant can end his or her participation in the study at any time during the recruitment or study process without negative consequences.

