Three: Immediately after completing the recruitment meeting research staff will complete Informed consent with all participants who express interest in participation in the study. This meeting will take place in a private setting in the prison.

Fourth: Research staff will complete a screening interview immediately after the informed consent process with all potential subjects who agree to participate in the study after completing informed consent. The study screening interview will determine whether participants are eligible to participate in the study by screening for mental health diagnoses, criminogenic risk levels, and prior engagement in T4C.

Fifth: At the end of the screening interview potential participants will be informed whether they meet the study eligibility criteria. Participants who are found eligible for the study and agree to participate will be assigned to a study condition. During the RCT phase of the study, participants will be randomized into one of two conditions, the research intervention (T4C-MI) or the control condition (Standard prison treatment and programming). The research staff will randomly assign participants to a study condition by opening a sequentially numbered envelope and discussing the condition assignment with the participant. In order to be sure that interviews are not too long, the screening and baseline interviews will be broken into two separate interviews, conducted at least one day apart from each other. After randomization is complete the research staff will schedule a mutually agreed upon time to return to complete the baseline interview.

Six: Research staff will complete a baseline interview with all study participants. This interview will take place in a private location in the prison. The baseline interview will include a brief assessment of participant's neurocognitive functioning, clinical and criminal justice history, and baseline assessments of treatment targets and study outcomes. The baseline interview will take 60-90 minutes to complete.

Seven: Research staff will complete follow-up interviews with all study participants at 3-, 6 -months after the baseline interview. Each interview is expected to take 30-60 minutes to complete and will be conducted in a private setting in the prison. Participants' outcomes will also be assessed at 9 months post release using administrative data.

6.b Informed Consent

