9. STATISTICAL ANALYSIS

Given the preliminary nature of this study, statistical analyses of our outcomes will not be conclusive; rather we will examine the data for trends across time rather than relying exclusively on tests of statistical significance.

9.a. Primary Outcomes

The primary outcomes of this study are: Aggression, Receipt of Behavioral Infractions, and Time Spent in Administrative Segregation (see Appendix B).

9.b. Secondary Outcomes

The secondary outcomes of this study are those measures listed as Treatment Targets in the conceptual model: Interpersonal Problem Solving, Criminal Attitudes and Associates, and Levels of Impulsivity (see Appendix B).

9.c. Statistical Methods

Treatment Targets and Study Outcomes that are collected via a standardized measure (i.e. Social Problem Solving, Criminal Attitudes and Associates, Impulsivity, and Aggression) are collected at baseline as well as during follow-up periods (see Appendix A). Study Outcomes that are collected via administrative data (i.e. receipt of behavioral infractions and time spent in administrative segregation), however, are not collected as baseline, rather are summed cumulatively over the period extending from the 3-month follow-up period through the 9-month follow-up period.

To examine the impact of T4C-MI on study outcomes that are measured dichotomously and only collected during follow-up periods (i.e. receipt of disciplinary fractions and administrative segregation), we will use chi-square tests to examine between-group differences during the post-test period. To examine between-group post-test differences when these outcomes are measured as counts (i.e. number of behavioral infractions received and days spend in administrative segregation), nonparametric tests will be used to test differences in group medians (e.g. Mann-Whitney Test) and regressions that can accommodate count data (e.g. Poisson, negative binomial) will be employed.

For Treatment Targets and Study Outcomes that are measured continuously and collected at both baseline and follow-up periods (i.e. Social problem solving, impulsivity, criminal attitudes and associates, and aggression), we will use T-tests to examine between-group differences at posttest as well as mixed effects linear models where measurement occasion at level 1 is nested within the individual at level 2.

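### Group delivery in the T4C-MI arm has no counterpart in the planned analyses, so standard errors are too small if outcomes vary between treatment groups beyond what controls in the same facility and cycle share

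*Combined protocol and SAP*

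**What the plan says.** Section 5.a describes T4C-MI as "delivered in a closed-group format to 8-12 people up to twice a week over 12-14 weeks". Section 5.b says of the other arm: "People assigned to the control condition will receive standard prison treatment and programming". It lists crisis care, psychiatric evaluation and medication management, and individual counselling, and describes no study-formed groups. The footnote to Appendix A confirms that only the treatment arm is offered the intervention.

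Randomisation is by individual (section 6.a): "The research staff will randomly assign participants to a study condition by opening a sequentially numbered envelope". Enrolment is repeated over time: "Recruitment of study subjects will begin the month prior to the initiation of each intervention cycle". Section 3 allows up to four facilities, and 3.a aims for equal arms through blocks.

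Section 9.c plans t-tests and "mixed effects linear models where measurement occasion at level 1 is nested within the individual at level 2" for the scale measures. For infractions and segregation as yes/no outcomes it says "we will use chi-square tests to examine between-group differences during the post-test period"; as counts they get Mann-Whitney tests and Poisson or negative binomial regression. Mediation uses SEM and GSEM. None of these names a treatment group, cycle or facility. Section 9.d gives no ICC or design effect, and the appendices list no group identifier.

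**The concern.** The person-level random effect handles repeated measures on one participant. It does nothing for correlation between participants who sat in the same closed group for 12-14 weeks, with the same peers and sessions. That grouping exists by design in one arm only, so individual randomisation does not balance it out.

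If group membership moves outcomes, 56 treated participants carry less information than 56 independent ones, and p-values and any intervals built on the same standard errors look more precise than they are. Supplying information for the R01 power calculations is also a main purpose of the pilot under 9.d. A later trial of a group-delivered treatment needs a design effect, and the plan does not provide for collecting what would inform one.

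**Working it through.** **Plan's own figure.** Section 9.d states up to 112 participants without a significance level, power, effect size, SD or ICC, so there is no calculation to reproduce.

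**Inputs from the documents.** Up to 112 participants in equal arms: 112/2 = 56 per arm. Groups of 8-12: 56/12 = 4.7 and 56/8 = 7, so about 5-7 groups.

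**Assumptions.** Two-sided 5% level, full enrolment, complete data, equal total variance in the arms, and treated and control participants balanced within cycles. Of the total outcome variance, let *g* be the share specific to the treatment group and *f* the share common to everyone in a facility and cycle, whichever arm they are in. The documents give neither.

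**Formula.** With average group size m = Σn²/56, the true variance of the difference in arm means, relative to the variance assumed by an analysis that ignores grouping, is about

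ratio = 1 + (m − 1)·g/2 − f.

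The factor 1/2 is there because only one arm is grouped. Shared variance cancels from the arm difference, hence the minus sign. Approximate true size is 2·[1 − Φ(1.96/√ratio)].

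Group sizes: seven groups of 8 give m = 8. Four groups of 11 and one of 12 give m = (4·121 + 144)/56 = 11.2.

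**Case 1: no shared variance (f = 0), post-test t-test.**

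| g | ratio, m = 8 | ratio, m = 11.2 | true size |
|---|---|---|---|
| 0.01 | 1 + 7·0.01/2 = 1.035 | 1.051 | 5.4-5.6% |
| 0.05 | 1.175 | 1.255 | 7.1-8.0% |
| 0.10 | 1.350 | 1.511 | 9.2-11.1% |

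Simulation of the t-test at 56 per arm agrees: 7.2-8.0% at 0.05 and 9.2-11.6% at 0.10. The true standard error is larger by √1.175 − 1 = 8% to √1.255 − 1 = 12% at 0.05, and by 16-23% at 0.10.

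**Case 2: all correlation shared (g = 0).** The ratio is 0.95 at f = 0.05 and 0.90 at f = 0.10, so the unadjusted standard error is slightly too large. Simulated size is 4.1-4.6%.

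**Case 3: ICC of 0.10 split equally (f = g = 0.05).** The ratio is 1 + 0.175 − 0.05 = 1.125 at m = 8 and 1 + 0.25 − 0.05 = 1.20 at m = 11. Simulated size is 6.7-7.6%.

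**Break-even.** The unadjusted standard error is too small only when (m − 1)·g/2 exceeds f, that is g > 2f/(m − 1). This is g > 0.29f at m = 8 and g > 0.20f at m = 11.

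**Value for the R01.** With f = 0, the sample-size multiplier 1 + (m − 1)·g/2 for m = 8 and m = 12 is 1.04-1.06 at g = 0.01, 1.18-1.28 at 0.05 and 1.35-1.55 at 0.10. The pilot's own estimate would be weak: at a true ICC of 0.05 there is about a 35% chance of an estimate at or below zero, with a 95% sampling range of about −0.10 to 0.26.

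**The case against.** The strongest objection is that correlation among group-mates is not enough. Recruits for each cycle appear to be randomised together within a facility, so controls share the prison, the period and the local disciplinary practice. That part of the correlation largely cancels between arms. A reader might infer that any positive ICC among treated group-mates makes the standard errors too small; Case 2 shows that it need not. **This stands**, and it limits the point to treatment-specific variance. It also rules out the simple remedy of a group effect with each control as a singleton. When all the correlation is shared (0.05-0.10), that model's standard errors were 14-31% too large in simulation and its size fell to 1.6-2.7%.

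A second tempting reading is that the mixed model fares much worse than the t-test. Simulated sizes up to about 16% can be obtained, but they need an arm-by-time contrast that 9.c does not specify, an assumed within-person correlation of 0.7, an ICC of 0.10 and no shared variance. The documents support none of these as the expected case.

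Third, infractions and segregation are "summed cumulatively over the period extending from the 3-month follow-up period through the 9-month follow-up period", mostly after the 12-14-week groups have ended. Their treatment-specific ICC may therefore be low. This is fair for those two outcomes. Facility differences also matter more there, because with no baseline value a stable facility effect is not removed by a change contrast.

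Fourth, section 9 says that "statistical analyses of our outcomes will not be conclusive", and 9.d disclaims full hypothesis testing and effect-size estimation. This lowers the severity. It does not remove the point: 9.c still plans tests, section 9 only declines to rely on significance exclusively, and 9.d argues that the design makes significance more likely.

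Finally, an ICC from 5-7 groups is too imprecise to plan on. That is true, and it argues for a range of ICCs rather than for leaving the grouping out. It would also go too far to say that group membership will be lost: the documents list no identifier, but nothing says that the team will not know who was in which group.

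**Conclusion.** The point holds in conditional form, at low severity. The plan groups participants in one arm and analyses them as independent. Standard errors are too small if treatment-specific group variance is appreciable relative to any variance shared with concurrent controls. Point estimates are not biased by the omission.

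The t-test sizes of about 7-8% at ICC 0.05 and 9-12% at 0.10 are upper-end figures. They assume no shared facility or cycle variance, 56 per arm and 5-7 groups. Near 0.01 the effect is negligible, and with wholly shared correlation it reverses slightly. The direction under the stated condition is firm; the size cannot be fixed from the documents. No figure was derived for Poisson regression or the indirect effect in the mediation models.

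**What to change.** Record treatment group, cycle and facility for every participant; for controls, record cycle and facility.

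In 9.c:
- Add facility and cycle terms common to both arms to the mixed model and the count regressions.
- Add a treatment-group random effect in the T4C-MI arm only. In the mixed model it should act on the post-baseline occasions, with Satterthwaite or Kenward-Roger degrees of freedom. A group intercept over all occasions is not enough, because it cancels out of an arm-by-time contrast.
- Because 5-7 groups estimate this variance poorly, add a sensitivity analysis with the treatment-specific ICC fixed at 0.01, 0.05 and 0.10.
- State that the chi-square, Mann-Whitney, t-test and SEM/GSEM p-values ignore the grouping.
- Report the ICC with its interval, and plan the R01 over a range of ICCs rather than on this estimate.

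Minimum version: keep the two-level model, record the IDs, state the limitation and run the fixed-ICC sensitivity analysis.

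The cost is a few ID variables, SAP wording and a little more analysis, with no new participants or visits. The downside is somewhat wider intervals. For a group term alone, the lost degrees of freedom widen them by about 5-8% even at ICC 0. The added cost of the shared facility and cycle terms was not calculated.

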10. SAFETY ASSESSMENT

The Study PI will oversee the safety of the study. Research data will be reviewed in a timely manner. The PI will comply with all existing policies for both documenting and reporting unanticipated or adverse events associated with this study.

10.a. Data Safety Monitoring Plan

This is a small-scale, pilot study with a relatively small number of subjects, thus, in lieu of a Data and Safety Monitoring Board, the PI will perform the monitoring function as part of the general oversight and scientific leadership of the study. The risk of the research intervention – T4C-MI- is relatively low. Any untoward effects of study participation will become apparent to the PI through close monitoring of individual study subjects and communication with prison staff.

11. PARTICIPANT RIGHTS AND CONFIDENTIALITY

11.a. Participant Confidentiality and Security

Project data and information will be maintained at the School of Social Work (SOSW) in the Tate-Turner-Kuralt Building on the campus of the University of North Carolina at Chapel Hill. At the SOSW, a secure, password-protected computer file for all project materials will be established with access restricted to the research team. All data schedules and interview forms will be filed securely away in locked file cabinets. All personal computers are password protected and servers are located on lockable offices.

Study subjects will be assigned unique, study identifiers. A separate master list of study IDs will be kept separately. Once data collection is complete, all personal identifiers will be destroyed. Once personal identifiers are destroyed all study subjects will be identified only by a unique study identifier.

All study documents will be maintained in locked filing cabinets within locked offices. Additionally, a Certificate of Confidentiality will be obtained to protect subject information. All interviews will take place in private settings within the prison. Participants will be informed that they can choose not to answer question(s) and can stop an interview at any time.

11.b. Study Discontinuation

There are four reasons that the study staff would withdraw a person from the research intervention and study: (1) in the unlikely event that a study participant would become aggressive or combative during the research intervention or research interview they would be withdrawn from the study; (2) if a subject's participation in the research intervention or interviews caused undue levels of emotional distress, either as reported by the subject or as observed by the researchers; and (3) if a subject asks to be withdrawn or declines further participation in the research intervention or follow-up research interviews at any point (4) if a subject is transferred or released from the prison where the experimental intervention is being delivered.

12. APPENDIX A: Assessment and Data Collection

	Initial Meeting and Screening Interview*	Baseline Interview	Delivery of the Study Intervention*	Three-month follow-up Interview	Six-month follow-up Interview	Nine-month administrative records check**
Screening and Intervention Delivery						
Recruitment and Informed Consent	X					
Participant Demographic and Background Characteristics	X					
Eligibility Determination	X					
Randomization	X					
Study intervention			X			
Data Collection						
Social Problem Solving		X		X		
Criminal Attitudes and Associates		X		X		
Impulsivity		X		X		
Aggression		X		X	X	
Behavioral Infraction**						X
Administrative Segregation**						X

*Only individuals randomized to the treatment condition are offered to participate in the intervention. The study intervention lasts between 12-14 weeks in duration

**This data is collected via administrative data, not through face-to-face interviews as is the other study data.

13. APPENDIX B: Description of Study Measures

Outcome	Measure	Description	Citation
Primary Study Outcomes			
Aggression	Aggression Questionnaire - Short Form (AQ-Short)	A 12-item measure with four subscales: physical aggression, verbal aggression, anger, and hostility. Items are scored on a 5-point Likert scale.	Bryant FB, Smith BD. Aggression Questionnaire--Short Form. Psytests. 2001. doi:10.1037/t09754-000
Behavioral Infractions	From administrative data	Prison records will be used to ascertain the number of behavioral infractions participants incur.	n/a
Administrative Segregation	From administrative data	Prison records will be used to determine the length of time participants are confined in administrative segregation.	n/a

Secondary Outcomes			
Social Problem Solving	Social Problem-Solving Inventory - Revised, Long (SPSI-R:L)	A 52-item measure of problem-solving skills and problem orientation. Items are measured on a 7-point Likert scale. It has three scales that will be used in this analysis: problem orientation, problem solving skills, and social problem-solving inventory.	D'Zurilla TJ, Nezu AM, Maydeu-Olivares A (n.d). Social Problem-Solving Inventory - Revised. Psytests. doi:10.1037/t05068-000
Criminal Attitudes and Associates	Measure of Criminal Attitudes and Associates (MCAA)	A 46-item measure. Responses are recorded in an agree/disagree format. MCAA includes four scales: attitudes toward violence, sentiments of entitlement, antisocial intent, and associates.	Mills JF, Kroner DG, Forth AE. Measures of Criminal Attitudes and Associates (MCAA): development, factor structure, reliability, and validity. Assessment . 2002 Sep;9(3):240-53. PubMed ID: 12216781
Impulsivity	Barratt Impulsiveness Scale (BIS-11)	A 30 item self-report measure. Items scored on a 4-point Likert scale. It is comprised of six subscales including attention, cognitive instability, perseverance, self-control, motor impulsiveness, and cognitive complexity.	Patton JH, Stanford MS, Barratt ES. Factor structure of the Barratt impulsiveness scale. J Clin Psychol . 1995 Nov;51(6):768-74. PubMed ID: 8778124

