Study Phases	
(1) Study Recruitment and Informed Consent
 
A) Prison Staff will provide study personnel with list of potentially eligible participants.B) Study staff will invite potentially eligible participants to meet with them to discuss study. Study staff will complete informed consent with all potential participants who agree. 
(2) Study Screening- All potential participants who agree to participate in the study after informed consent is completed will participate in a screening interview to determine study eligibility.
 
(3) All participants who are found eligible at the end of the screening interviews will be randomized to one of the two study arms (e.g. experimental or control condition). These individuals will make up the study sample
 
(4) Baseline interviews will be completed with all study participants.
 
(5) Study participants who are randomized into the experimental condition will participate in the study intervention. Those who are randomized into the control condition will receive standard prison treatment and programming.
 
(6) Follow up: Study participants will participate in follow-up interviews at 3- and 6- months post-baseline.
 
(7) Administrative data related to behavioral infractions and administrative segregation will be gathered at 9-months post-baseline.

Screening	
Study Treatment	
Follow-Up	

The statistical analyses of this study will explore the treatment effect of the study intervention on the study outcomes (aggression, receipt of behavioral infractions, and time spent in administrative segregation) and the study treatment targets (impulsivity, social problem solving, and criminal attitudes and associates). Additionally, mediation analyses will be conducted to explore whether treatment effects on study outcomes operate indirectly through study treatment targets.

DATA AND SAFETY MONITORING PLAN	This is a small-scale, pilot study with a relatively small number of subjects; thus, in lieu of a Data and Safety Monitoring Board, the PI will perform the monitoring function as part of the general oversight and scientific leadership of the study
---------------------------------	---

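### Read as written, section 11.b ends study participation for anyone who declines or is removed from the T4C-MI group, which lowers recorded retention by rule in that arm only

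*Combined protocol and SAP*

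**What the plan says.** Section 11.b introduces its list with: "There are four reasons that the study staff would withdraw a person from the research intervention and study". Reason 1 is the case, described there as unlikely, in which "a study participant would become aggressive or combative during the research intervention or research interview they would be withdrawn from the study". Reason 2 is undue distress from the intervention or the interviews. Reason 3 includes anyone who "declines further participation in the research intervention or follow-up research interviews at any point". Reason 4 is transfer or release from the prison where the intervention is delivered.

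A footnote to Appendix A says: "Only individuals randomized to the treatment condition are offered to participate in the intervention".

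Other places suggest that everyone randomised is followed:

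- The Study Phases entry of the synopsis says of those found eligible and randomised: "These individuals will make up the study sample".
- Section 6 says: "All participants who are randomized to either study condition complete three additional follow up interviews".
- Appendix A schedules a nine-month check of infraction and segregation records and notes: "This data is collected via administrative data, not through face-to-face interviews as is the other study data".

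None of these says what happens after a withdrawal. Section 9.c lists the tests and models but names no analysis set and no treatment of withdrawn participants. Section 9.d gives the collection of attrition and retention data, for planning a larger trial (an R01), as part of the main purpose of the study.

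**The concern.** The protocol has no status for a person who is off the intervention but still in follow-up. Stopping the group and being lost to the study become one event, although they answer different questions. The first concerns acceptability of T4C-MI; the second concerns whether outcomes can be collected in this setting.

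Controls are not offered the group, so they cannot be withdrawn for declining it or for conduct or distress during it. Interview-based triggers, transfer and release apply to both arms. An arm difference in retention can therefore appear because of the rule, even if people in both arms are equally willing to be interviewed.

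A second concern is conditional. If outcomes are also dropped after withdrawal, removal for aggression selects on behaviour that overlaps a primary outcome. T4C-MI participants have more study contacts at which it could be triggered, so the selection could favour T4C-MI.

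**Working it through.** **No plan figure to reproduce.** The 112 in section 9.d is a ceiling. No attrition, adherence or withdrawal rate is attached to it.

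**Inputs from the documents**

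- Maximum sample 112 (9.d), allocated equally (3.a): 112 / 2 = 56 per arm.
- Up to 25 group sessions, T4C-MI arm only (5.a, Appendix A).
- Three interviews after randomisation in both arms: baseline, 3 and 6 months (6).
- Contacts at which a session- or interview-based trigger could arise: 25 + 3 = 28 in T4C-MI, 3 in controls.

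**Assumed inputs**

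- r = share in each arm who would complete interviews if everyone were followed: 90%, with 80% as a check.
- s = share of T4C-MI participants who formally decline or are removed from the group: 10%, 20% or 30%.

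**Formulas, with 11.b read as written**

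- Control retention = r.
- Ceiling on T4C-MI retention = 1 − s. Of 56 that is 50.4, 44.8 or 39.2, or about 50, 45 or 39 people.
- T4C-MI retention if stopping the group is independent of interview loss = r(1 − s).
- T4C-MI retention if the two overlap as far as possible = min(r, 1 − s).

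| r | s | Control | T4C-MI, independent | Gap (points) | T4C-MI, full overlap | Gap (points) |
|---|---|---|---|---|---|---|
| 90% | 10% | 90% | 0.9 × 0.9 = 81% | 9 | 90% | 0 |
| 90% | 20% | 90% | 0.9 × 0.8 = 72% | 18 | 80% | 10 |
| 90% | 30% | 90% | 0.9 × 0.7 = 63% | 27 | 70% | 20 |
| 80% | 10% | 80% | 0.8 × 0.9 = 72% | 8 | 80% | 0 |
| 80% | 20% | 80% | 0.8 × 0.8 = 64% | 16 | 80% | 0 |
| 80% | 30% | 80% | 0.8 × 0.7 = 56% | 24 | 70% | 10 |

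If stopping the group did not end follow-up, T4C-MI retention would equal r in every row.

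**Could records still be obtained?** Infraction and segregation data come from prison records, not interviews. Section 4.a requires at least 12 months left on the sentence at screening, and follow-up ends 9 months after baseline. On timing, section 6.a says: "Recruitment of study subjects will begin the month prior to the initiation of each intervention cycle". With up to about a month between screening and baseline, 12 − 1 − 9 leaves about 2 months of slack. Release inside the window should therefore be mainly early release. Transfer need not end access if records can be obtained across the state system, which is an assumption.

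**The case against.** The strongest reply is that reason 3 can be read item by item: whoever declines the group leaves the group, and whoever declines interviews leaves the interviews. The synopsis, section 6 and Appendix A fit that reading. A visit schedule for everyone alongside a list of withdrawal reasons is also ordinary protocol structure. This reading is possible. But the opening sentence of 11.b governs all four reasons and names both the intervention and the study, and no other section restores follow-up after the group is stopped. The sections should be reconciled.

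It can also be said that the team could break retention down by reason. The four reasons do not allow this: declining the group and declining interviews share reason 3. Once interviews stop, nobody learns whether the person would have continued.

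Other parts of the reply stand:

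- Sections 9 and 9.d disclaim conclusive testing, so bias in the treatment comparison matters less here.
- The mixed model can use partial interview data.
- The consent and HIPAA forms may address data collection after withdrawal; they were not available.
- If the larger trial kept the same rule, the retention observed here would be the relevant planning figure.

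A reader might infer that T4C-MI retention is capped at session attendance. It is not: missing single sessions is not a withdrawal reason. The ceiling is the share who have not formally declined or been removed from the group.

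**Conclusion.** The point holds for 11.b as written and should be fixed. The rule discards retention information, and possibly outcomes, that could still be obtained, through a route that exists in one arm only. It does so in a trial that names retention as part of its main purpose.

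The size is illustrative because r and s are both assumed. With r = 90% and s = 10% to 30%, the arm gap created by the rule is 9 to 27 points under independence and 0 to 20 points with full overlap. The range includes no effect.

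Two stronger inferences are tempting and unsupported. A reader might conclude that the larger trial would be over-enrolled by a calculable amount. The documents do not say how retention will be carried forward or whether arms will be pooled, and two of the three primary outcomes come from records rather than interviews. A reader might also conclude that the comparison is biased towards T4C-MI. That requires outcomes to be dropped after withdrawal, which the plan neither states nor excludes. The size of any such bias cannot be derived from the documents, and 11.b calls removal for aggression unlikely.

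**What to change.** 1. Reword 11.b so that stopping the group and leaving the study are separate events, and so that declining only the group does not end the scheduled interviews. Leave the grounds for stopping the group unchanged. Align the synopsis, section 6 and Appendix A with the new text.
2. Retrieve the 3-to-9-month infraction and segregation records for every randomised participant while in state custody, including those withdrawn or transferred, unless consent or authorization is revoked. Where release shortens the window, use log(custody days) as an offset in the count model and report the number affected by arm.
3. State in 9.c that all randomised participants are analysed by assigned arm.
4. Report stopping the group and loss to follow-up as separate figures, by arm and reason.

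**Cost.** A few sentences of protocol text, a little more record retrieval and a few more interviews. It depends on access to records across facilities and on what the consent and HIPAA forms allow.

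**Limit.** Aggression-questionnaire scores after removal for aggression or distress stay missing under this change. Analysis by assigned arm cannot restore them, so their number should be reported by arm.
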